Specific Aim 1: To compare abstinence rates among AA non-daily smokers receiving either smoking cessation counseling (C) or smoking cessation counseling in combination with NRT (C+NRT). Hypothesis: Participants randomized to C+NRT will have significantly higher biochemically verified smoking abstinence than participants randomized to C at 12 weeks end of treatment (primary outcome) and at 26 week follow-up. Analytic strategy: The chi-square test will be used to compare the verified abstinence rates at Week 12 (primary cessation endpoint) and Week 26 (secondary cessation endpoint) between C and C+NRT. For our primary comparison, those lost to follow-up will be considered as smokers. Assuming the expected treatment effect, we will descriptively examine the cessation rate within the C+NRT group by choice of NRT. A statistical comparison will not be conducted as we do not know a priori who will choose what and the choice will not be random. We also will look at completers only and will utilize multiple imputation techniques to ensure valid comparisons between the two groups if the loss to follow-up is not random. Secondly, we will utilize Generalize Estimating Equation methodology to longitudinally compare verified abstinence. We will then examine the effects

of the covariates and patient and provider outcomes listed in the measurement table above on this endpoint by utilizing best subsets selection techniques. Our goal is to identify a final model utilizing the smallest subset of covariates that describes cessation over the length of the study. Given the sample size and expected cessation rate, we anticipate a model that contains at most six covariates. We expect no difference in the distribution of demographic and smoking history covariates between groups and we will not statistically compare those as per CONSORT recommendations for randomized clinical trials. Within the NRT treatment group, we will examine the effect of NRT adherence over the first 12 weeks on verified cessation using logistic regression.

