Specific Aim 2: To compare patient- and provider-desired outcomes -- e.g., nicotine intake, carcinogen exposure, number of days abstinent, and side effects – among AA non-daily smokers receiving C versus C+NRT and, within the C+NRT group, examine the choice of NRT and use during the treatment period. Hypothesis: Participants randomized to C+NRT will demonstrate significantly greater reductions in nicotine intake and carcinogen exposure and significantly more days abstinent, while experiencing no differences in side effects as participants randomized to C. Analytic strategy: We will utilize linear mixed models to longitudinally (week 12 and 26) compare nicotine and carcinogen exposure between the two groups, then subsequently examine the effects of the covariates listed in the measurement table above using a best subsets selection method for both nicotine and carcinogen exposure independently. A generalized linear mixed model approach will be used to model days abstinent, controlling for number of days in study, to assess the effect of treatment on this endpoint and best subsets selection will be used to examine the effects of covariates on this endpoint. For each of these models, based upon the sample size, we anticipate that ten to twelve covariates could be included in a final model. We will compare the prevalence of any side effect as well as each specific side effect, from baseline to week 12, between the two groups using the chi-square test. If there is a global difference we will examine, within the NRT group, if type of NRT impacts the side effect profile. Within the NRT group we will descriptively summarize the number and percent of subjects who choose each type of NRT. Subsequently we will describe and descriptively compare the percent of subjects within each of these subgroups who use the NRT of choice during the treatment period (i.e., percent of patients within the patch, gum, and lozenge groups who used the medication).

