Smoking abstinence at Wk 12 (primary cessation outcome) and Wk 26 (secondary cessation outcome). Biochemically confirmed at Wk 12 using urine anabasine and anatabine, with the recommended cut-off of 2 ng/ml to differentiate smokers from non-smokers. ⁵⁰ These tobacco alkaloids are considered the gold standard for confirming abstinence when cotinine measurements are not valid – i.e., detectable levels of cotinine could reflect NRT use or smoking. ⁵⁰ Biochemically confirmed at Wk 26 using urinary cotinine, the proximate metabolite of nicotine, with the recommended cut-off of 50 ng/ml used to differentiate smokers from non-smokers. ⁵¹ Time Points: Wk 12, 26
Secondary Patient- and Provider-Derived Outcomes (Aim 2)
Nicotine intake (total nicotine equivalents/creatinine). Assessed by urine; quantified by examining the sum of four of the major nicotine metabolites (cotinine + cotinine-glucuronide + trans-3'-hydroxycotinine + 3HC-glucuronide) to creatinine ratio using procedures described by [name] (consultant). ⁵¹ Total nicotine equivalents/creatinine represents the current gold standard for estimating nicotine intake/exposure from tobacco. ⁵⁷ To ensure that nicotine metabolites detected at Wk 12 are a result of tobacco exposure and not NRT use, we will schedule the urine collection for 7 days after the last dose of NRT. This 7-day time frame is more than adequate given the 15-20 hour (3-4 day) elimination half-life of cotinine and accounts for the substantial individual variability in the rate of elimination of nicotine. ⁵⁸ Time Points: Wks 0,12,26
Carcinogen exposure [NNAL, PAH]. Assessed by urine; quantified by examining NNAL (4-(methylnitrosamino)-1-(3)pyridyl-1-butanol) and polycyclic aromatic hydrocarbons (PAH) and specifically, 1-hydroxypyrene (1-HOP), using procedures described by [name] (consultant). ⁴⁰ While there are >70 established carcinogens in tobacco, NNAL and PAH are widely considered to be among the most important causative agents in the development of lung and esophageal cancer ^{38,39,59} and reflect the current gold standard for estimating carcinogen exposure from tobacco products. Time Points: Wks 0,12,26
Days Abstinent. Cumulative number of days abstinent Time Points: Wks 1,4,8,10,12
NRT adherence. 3-day recall of NRT use (C+NRT only) -- i.e., pieces of gum, lozenge, or number of patches used in the last 3 Time Points: Wks 4,8,12

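### The Aim 1 best-subsets step admits post-randomisation outcomes as predictors of abstinence and does not keep treatment in, so the final cessation model can be partly circular and can omit treatment

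*Combined protocol and SAP*

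**What the plan says.** Section II.C, Specific Aim 1, sets the order of analysis. Chi-square tests compare verified abstinence between the arms at Week 12 (primary) and Week 26, and a GEE then compares the arms longitudinally. After that the plan examines the effects "of the covariates and patient and provider outcomes listed in the measurement table above on this endpoint by utilizing best subsets selection techniques". The purpose is stated: "Our goal is to identify a final model utilizing the smallest subset of covariates that describes cessation over the length of the study". So is the expected size: "we anticipate a model that contains at most six covariates". The text names no selection criterion, sets no time point for the predictors, and does not say that any term is kept.

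The table in question is Measure and Assessment Time Points in section II.E. Its patient- and provider-derived outcomes are:

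| Outcome | Weeks measured | Week 0 value |
|---|---|---|
| Nicotine intake | 0, 12, 26 | yes |
| Carcinogen exposure | 0, 12, 26 | yes |
| Days abstinent | 1, 4, 8, 10, 12 | no |
| NRT adherence (C+NRT only) | 4, 8, 12 | no |
| Side effects (seven symptoms) | 4, 8, 12 | no |

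The covariate block of the same table, marked for all three aims, lists treatment assignment and NRT choice alongside demographics and smoking history. The matching Aim 2 sentence draws on covariates only: "then subsequently examine the effects of the covariates listed in the measurement table above using a best subsets selection method".

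**The concern.** A model of who quits is useful if its predictors are known before quitting and if treatment can be read from it. The Aim 1 pool, taken as written, guarantees neither.

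Some candidates restate the endpoint or share its assay. Others are effects of treatment by the plan's own Aim 2 hypothesis, which expects C+NRT to show "significantly greater reductions in nicotine intake and carcinogen exposure and significantly more days abstinent". Adherence is undefined in the counselling arm, so a between-arm model that includes it either loses that arm or uses adherence as a stand-in for treatment. Treatment itself sits in the pool open to selection, and a search for the smallest subset may discard it once a near-copy of the outcome is available.

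At stake is the interpretation of the secondary final model, in a trial meant to inform treatment guidelines. The primary result does not depend on it.

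**Working it through.** **1. The plan's own figures.** Inputs from section II.C: 128 and 256 participants, 10% versus 20%, 22.5% or 25%, 5% type 1 error (taken as two-sided). With power = Φ[(Δ − 1.96·SE₀)/SE₁], SE₀ pooled and SE₁ unpooled, the 22.5% case has pooled rate (12.8 + 57.6)/384 = 0.1833, SE₀ = 0.0419 and SE₁ = 0.0372. Then (0.125 − 0.0821)/0.0372 = 1.15, which gives 87.6%. The other two cases give 71.7% and 95.7%. The stated 71%, 87% and 95% reproduce and are not in dispute.

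**2. Overlap of candidates with the endpoint.** The endpoint is 7-day abstinence.
- "Days Abstinent. Cumulative number of days abstinent Time Points: Wks 1,4,8,10,12". The count to Week 12 includes the seven days that define the Week 12 endpoint.
- "Nicotine intake (total nicotine equivalents/creatinine). Assessed by urine; quantified by examining the sum of four of the major nicotine metabolites". Cotinine is one of the four, and Week 26 abstinence is verified by urinary cotinine with a 50 ng/ml cut-off. At Week 12, verified by anabasine and anatabine, intake is a correlate of abstinence rather than a component of it.
- Week 0 intake has neither problem. Section I.B names nicotine intake among the patient characteristics of interest.

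**3. Room in the model.** Expected Week 12 quitters are 12.8 + 51.2 = 64 to 12.8 + 64 = 76.8, or 10.7 to 12.8 per term for six terms. Counted singly, days abstinent, adherence and seven symptoms make nine candidates that exist only after randomisation.

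**4. Retention of treatment without any such candidate.** BIC keeps a single term if the likelihood-ratio statistic exceeds ln 384 = 5.95, and AIC if it exceeds 2. Putting √5.95 = 2.44 and √2 = 1.41 in place of 1.96 in step 1 gives about 73% and 96% at 22.5%. Simulation (400 trials, all subsets, logistic regression) gives 77% and 96%. So BIC alone loses treatment in roughly a quarter of trials.

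**5. Retention when one is added.** Assumed candidates: treatment, baseline smoking days (log odds 0.5 per SD), two or three noise covariates and the marker. The GEE version has two visits at the same rates, an independence working correlation and time forced in.

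Anchor for intake: section I.B reports cotinine of 807.8 ng/mg in African American non-daily smokers. Against the cut-off, 807.8/50 = 16.2 and ln 16.2 = 2.78, which is 1.4 to 2.8 SD for an assumed log SD of 2 to 1 and creatinine of 1 mg/ml. A weaker 0.5 SD was added.

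Anchor for days abstinent: a non-quitter smoking 13 of 30 days has 84 × 17/30 = 47.6 smoke-free days. A Week 12 quitter has 77 × 17/30 + 7 = 50.6 (quit day 77) to 84 (quit day 0). With baseline days uniform on 4 to 27, the SD is (84/30) × 23/√12 = 18.6, so the gap is 3.0/18.6 = 0.2 to 36.4/18.6 = 2.0 SD. Quit day was drawn uniformly on 0 to 77, with an assumed drift in non-quitters' smoking.

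Treatment retained, without → with the marker:

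| Marker and criterion | 10% v 20% | 10% v 22.5% | 10% v 25% |
|---|---|---|---|
| Intake, BIC | – | 77% → 74–25% | – |
| Intake, AIC | – | 96% → 95–63% | – |
| Intake, two-visit GEE, QIC | 95% → 94–64% | 99% → 99–75% | 100% → 100–85% |
| Days abstinent, BIC | 62% → 58–19% | 80% → 73–28% | 91% → 87–39% |
| Days abstinent, AIC | – | 98% → 95–71% | – |

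The simulation error on 77% is √(0.77 × 0.23/400) = 2.1 points, so the losses for intake at the weak end are not distinguishable from noise.

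**6. The treatment estimate.** If treatment moves the marker only through quitting, the log odds ratio does not shrink: 1.01 versus 1.00–1.03 with intake, 1.04 versus 1.04 with days abstinent. If NRT is also assumed to lower non-abstainers' intake by 0.25 SD, it falls from 1.01 to 0.93–0.60. If the marker instead tracks a latent propensity to abstain (noise SD 1, 200 trials), it falls from 0.95 to 0.63.

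**The case against.** The strongest reply is that little hangs on this step. The Aim 1 hypothesis is tested by chi-square and by a GEE before any selection, and the later model is only meant to describe cessation. That is right, and it limits the severity.

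A second reply is that the step follows a between-arm GEE and may simply add terms to a model that already holds treatment. The wording allows this, but nothing states it, and treatment is listed among the covariates to be selected. Even on that reading the circular candidates remain. Nor can baseline values be taken as implied, since three of the five outcomes have none.

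The illustration is open to fair criticism:
- Much of the loss under BIC comes from the criterion, before any post-randomisation candidate enters.
- The 807.8 figure and the 13 days are not labelled as means or medians, and a uniform 4 to 27 has mean 15.5, not 13.
- The intake anchor uses cotinine alone, compares smokers with a cut-off rather than with quitters, and applies a Week 26 assay to both visits.
- Symptoms might enter as one any-side-effect term, adherence already has its own within-arm regression, and six terms is an expectation, not a firm cap.
- Whether the treatment estimate is attenuated depends on the marker model chosen.
- The Aim 2 contrast is weak, because the Aim 2 endpoints come from the same outcome block.

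These points stand against the percentages and the Aim 2 comparison. They do not touch the reading of the text in step 2.

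**Conclusion.** The concern holds. Followed literally, the Aim 1 rule admits predictors that overlap the endpoint or follow from treatment, and it leaves treatment open to removal. This goes beyond missing detail, because the outcome block is named as part of the pool.

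How often treatment would be lost cannot be fixed from the documents. At 10% versus 22.5% it ranges from no detectable change with a weak intake marker to retention of about a quarter under BIC with a strong one. Those figures rest on the assumed criterion, separation and covariate set. Bias in the treatment estimate is possible but not established.

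Only the secondary final model is affected. The Week 12 and Week 26 tests, the initial GEE, the power statement and the Aim 3 tree are not touched by this point. The change should be made, but the primary analysis does not wait on it.

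**What to change.** In section II.C, Specific Aim 1:
- Limit the selection candidates to Week 0 values: demographics, smoking history, and Week 0 nicotine and carcinogen biomarkers.
- State that treatment arm and time are in every candidate GEE model.
- Keep NRT choice and adherence out of between-arm models. The within-arm adherence regression already planned can stay.
- Name the selection criterion.
- Report links between quitting and post-randomisation exposure or days abstinent as a separately labelled descriptive or mediation analysis, so that the exploratory interest is kept.

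The cost is one or two sentences in the analysis plan. No data, visits or participant burden are added.

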C. Sample size, statistical methods, and power calculation

384 AA non-daily smokers will be randomized. We will use 2:1 randomization; for every patient randomized to C, two will be randomized to C+NRT (see Figure). Randomization will be determined by computer-generated random numbers generated by [name]. Randomization assignments will be placed in sealed envelopes by a member of [name] team with sequential study ID numbers. After baseline data collection has been completed, the research assistant will select the sequential study ID number from the sealed envelope to determine the randomization assignment.

The maximum number of participants enrolled in C will be 128 and the maximum number enrolled in C+NRT will be 256. Our sample size is based on our primary outcome, biochemically confirmed point-prevalence abstinence at Week 12 using an intent-to-treat approach. Based on treatment studies with AA light smokers who have received tobacco treatment guideline-based counseling and no pharmacotherapy, we expect a 10% point prevalence abstinence rate in the C group and a 20-25% point prevalence abstinence rate in the C+NRT group based on recent meta-analyses and studies examining the effectiveness of these medications in AA light smokers.^{11,28,45,46} Using the chi-square test, along with the assumptions above, 256 participants in the C+NRT group and 128 participants in the C group (n=384), we will have 95% power to detect an increase from 10% to 25% in cessation at Week 12 between C and C+NRT, 87% power to detect a and increase from 10% to 22.5%, and 71% power to detect an increase from 10% to 20% with a type 1 error rate of 5%.

Analysis Plan for Each Aim

All primary analyses on smoking cessation will be conducted using intent-to-treat and will code those lost to follow-up as smokers. Subsequently we will evaluate the missing data pattern. If there is a differential loss based upon group, multiple imputation techniques will also be used.

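### The Aim 1 covariate model searches about 23 items, some partly restating abstinence, with 64–77 expected quitters and no allowance for the search

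*Combined protocol and SAP*

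**What the plan says.** Section II.C, Specific Aim 1, sets an order: a chi-square test of verified abstinence at Weeks 12 and 26, then a longitudinal GEE comparison, and only then a look at the effects "of the covariates and patient and provider outcomes listed in the measurement table above on this endpoint by utilizing best subsets selection techniques". The aim of that last step is a parsimonious model of cessation over the study. Its size is tied to the sample size and the expected quit rate: "we anticipate a model that contains at most six covariates". No selection criterion, shrinkage, resampling or exploratory label is given, and treatment is not said to be kept in the model.

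The candidates are in the Measure and Assessment Time Points table in Section II.E. It lists demographics, smoking history, treatment (assignment and NRT product chosen) and the Aim 2 patient and provider outcomes.

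Specific Aim 3, on the same Week 12 cessation endpoint, does plan 10-fold cross-validation and a bootstrap for its tree. Specific Aim 2 also uses best subsets, on the covariates only, and says "ten to twelve covariates could be included in a final model".

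**The concern.** Two features of the search can mislead.

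- **Size of the search.** Limiting the final model to six terms does not limit how many items competed for those places. Terms picked because they fit best look stronger in the same data than they would in new data, and nothing planned for this model measures or removes that optimism.
- **Content of the pool.** Some candidates are measured after randomization and are close to abstinence itself. They would be selected because they overlap the endpoint, and could crowd out baseline predictors or treatment assignment.

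The result will be read as a list of who quits. Section I.C says the findings should help patients and providers judge individual chances of success from personal characteristics, so an unstable or circular predictor list has practical consequences.

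**Working it through.** **1. The plan's own figures.** Inputs from Section II.C: 128 in C, 256 in C+NRT, 2:1 allocation, and "we expect a 10% point prevalence abstinence rate in the C group and a 20-25% point prevalence abstinence rate in the C+NRT group". For the two-sided 5% chi-square test with pooled variance and no continuity correction:

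power = Φ{[Δ − 1.96·√(p̄(1−p̄)(1/128+1/256))] / √(p₁(1−p₁)/128 + p₂(1−p₂)/256)}

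For 10% vs 20%: p̄ = 64/384 = 0.1667, and (0.10 − 0.0791)/0.0364 = 0.574, so power is 71.7%. The other two cases give 87.6% (22.5%) and 95.7% (25%). The plan states 71%, 87% and 95%, so its inputs reproduce.

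**2. Expected Week 12 quitters.** 128×0.10 + 256×0.20 = 12.8 + 51.2 = 64.0; 128×0.10 + 256×0.25 = 12.8 + 64.0 = 76.8. Those lost to follow-up count as smokers, so the denominator stays at 384.

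**3. Candidates.** Demographics 6; smoking history 9; treatment 2; outcomes 6 (nicotine intake, NNAL, 1-HOP, days abstinent, NRT adherence, side effects as one item). Total 6 + 9 + 2 + 6 = 23, and more if the seven listed symptoms are counted singly.

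**4. Quitters per variable.**

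| Basis | 64 quitters | 76.8 quitters |
|---|---|---|
| Six final terms | 10.7 | 12.8 |
| 15 baseline variables | 4.3 | 5.1 |
| All 23 items | 2.8 | 3.3 |

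Best subsets of up to six from 23 compares 145,499 models, counting the empty one.

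**5. Effect of the search on noise.** Simulations used n = 384, independent noise candidates and the Week 12 outcome.

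- 20 candidates, about 17% quitting, six with the largest mean differences kept (600 trials): 0.95 kept terms per trial at p<0.05, so 0.95/6 = 16% per kept term instead of 5%. Apparent AUC was 0.65, against 0.50 on new data.
- Treatment forced in, 22 noise candidates, full subset search, six kept (1,200 trials per setting): 1.25 to 1.29 such terms, so 1.25/6 = 21% to 1.29/6 = 22% per kept term.
- The same with 15 noise candidates: 0.82/6 to 0.83/6, about 14%.

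**6. Comparators.** The chance of at least one p<0.05 among 20 noise variables with no selection is 1 − 0.95²⁰ = 64%; simulated full models gave 63% to 69%. Keeping the best six gave 59% to 66%. That summary therefore does not isolate the search; the per-term rate does. Six prespecified noise variables already give an apparent AUC of 0.59, so the search accounts for about 0.65 − 0.59 = 0.06 of the optimism, and ordinary overfitting for the rest.

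**7. Candidates set beside the endpoint (Section II.E).**

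- Week 26 abstinence is defined by urinary cotinine with a 50 ng/ml cut-off. Nicotine intake is a creatinine-adjusted sum of four metabolites, one of which is cotinine. At Week 26 the predictor contains the analyte that defines the outcome.
- Days abstinent is a running count through Week 12. The Week 12 endpoint is 7-day abstinence, so those days enter both.
- NRT choice and adherence exist only in C+NRT and are undefined for the 128 C participants.

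**The case against.** The plan promises no p-values or intervals for this model, and six is a ceiling, not a target. A reader might infer that a ten-events rule is stated and broken. It is not stated; six merely fits such a rule (64/6 = 10.7), and the rule is only a rule of thumb. A reader might also take the roughly 60% chance of a false term as proof of search bias; step 6 shows that it is not.

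The size of the effect depends on a criterion that the plan does not give. With 22 noise candidates, at least one false term at p<0.05 appears in 72% to 73% of trials under AIC but 30% under BIC. This stands, but BIC is not a cure for the inference: it kept 0.34 to 0.36 noise terms per trial, and to two decimals the same number had p<0.05.

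The simulations use independent candidates and one time point, whereas the plan uses GEE. Week 26 records come from the same people, so independent information should stay near this range, but that is an assumption. Noise simulations also say nothing about nicotine intake or days abstinent, which would enter through overlap and not by chance; that objection rests on the definitions alone. Week 0 biomarker values would not be circular, but the plan names these items as outcomes and gives no time point for their use here.

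The plan analyses adherence within C+NRT and rules out a statistical comparison by product, so the intended pool may be smaller than 23. The text does not say so.

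Aim 2 might seem to share the whole problem. It does not: it searches covariates only, and its endpoints are biomarkers and day counts, with 384/17 = 22.6 participants per covariate.

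**Conclusion.** The point holds for the Aim 1 secondary covariate model and should be corrected. About 23 items compete on 64 to 77 expected quitters, the limit of six applies only after the search, and no optimism correction is planned, although Aim 3 has one for the same endpoint. Some candidates partly restate abstinence or exist in one arm only. If ordinary inference is attached to the selected terms, noise terms would reach p<0.05 about 16% of the time (about 21% under a full search of 22) instead of 5%, and apparent AUC would be about 0.65 with no true signal. These sizes assume independent noise candidates, six terms kept and the plan's expected quit rates.

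A reader might go further and infer that the trial's treatment result is at risk. The documents do not support that: the chi-square test and the GEE treatment comparison come before the selection and do not depend on it.

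**What to change.** In Section II.C, Specific Aim 1:

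- Force treatment assignment into the model.
- Limit candidates to the 15 baseline demographic and smoking-history variables, and state the selection criterion.
- Repeat the whole selection in bootstrap samples; a penalized model (LASSO or elastic net) is an acceptable alternative. The baseline restriction alone is not enough, since about 14% of kept noise terms still reach p<0.05.
- Report selection frequencies and optimism-corrected discrimination.
- Label the model exploratory and give no unadjusted post-selection p-values.

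For Aim 2, bootstrapping the selection is optional. The cost is wording and a little more programming, with no new data or participants. The downside is that fewer covariates will look significant.
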